5.6 Subject identification

Study subjects will be identified by a number and the initials of their name.

The initials of the subject of study will be obtained starting with the first letter of the name, followed by the first letter of the first surname and the first letter of the second surname, obtaining a maximum of three letters. In case the person has two names or a compound surname, the first letter will always be used.

Example:

Name: Ariel Daniel Mercado Carrizalez.

Initials: AMC.

Name: Juan De la Torre Orozco.

[figure not shown]
Initials: JDO.

During the counting stage, you will be assigned a participant number consecutively, using 3 consecutive digits.

Once the subject has been selected, they will be assigned a randomization number, which will be used to identify them throughout the study. This code will consist of eight numbers in the following order from left to right:

- three digits of the molecule under study according to the name given by the sponsor.
- two digits corresponding to the research center number.
- three digits of the consecutive number assigned to its inclusion in the research center.

Example of randomization number:

6. Investigational product

6.1 Managed Products

6.1.1 Investigational product

- Generic name: Sodium Hyaluronate.
- Distinctive name: PRO-149.
- Active ingredients: Sodium Hyaluronate 3%.

- Pharmaceutical form: Viscoelastic solution.
- Presentation: prefilled syringe, 1 cc.
- Prepared by: Laboratorios Sophia, S.A. de C.V.
- Solution description: Clear solution, free of visible particles.

6.1.2 Reference product

- Generic name: Sodium Hyaluronate.
- Distinctive name: Healon® EndoCoat.
- Active ingredients: Sodium Hyaluronate 3%.
- Excipients: sodium chloride, potassium chloride, calcium chloride, magnesium chloride, sodium acetate, sodium citrate, dibasic sodium phosphate, monobasic sodium phosphate, water for the manufacture of injectables.
- Pharmaceutical form: Viscoelastic solution.
- Presentation: 0.85 cc prefilled syringe.
- Prepared by: Johnson & Johnson Vision Surgical, Santa Ana, CA, USA.
- Solution description: Clear solution, free of visible particles.

6.1.2.1 *Justification of the reference product*

Healon® EndoCoat is a commercially available OVD with a previously described safety and efficacy profile.

6.1.3 Dosage of investigational products

As much as is necessary for the formation of spaces and the performance of surgical maneuvers.

6.1.3.1 *Justification of the dose*

There is no standardized dose for OVDs; each case is customized according to the anatomical characteristics and surgical needs.

6.1.4 Concomitant treatment

Both groups will be treated with:

- Generic name: Ciprofloxacin 0.3%/Dexamethasone 0.1%
- Distinctive name: Sophixin DX
- Active ingredients: Ciprofloxacin 0.3%, Dexamethasone 0.1%.
- Pharmaceutical form: Ophthalmic solution.
- Presentation: 5 mL dropper bottle.
- Prepared by: Laboratorios Sophia, S.A. de C.V.
- Solution description: Clear solution, free of visible particles.

- Dosage: 1 drop every 4 hours for 10 days in the operated eye.

6.2 Storage and handling of investigational products at the study center

Delivery will be made via a courier service contracted by the sponsor, specifically selected for this purpose, to the address of the research center in accordance with the study plan.

Reception will be carried out by the assigned research team staff. They must verify the condition of the primary packaging (box). If it shows alterations or defects in its integrity that, in their judgment, could have damaged the contents, they must report this to the sponsor. If the package shows no significant defects, they will proceed to open it.

Inside the shipment, you must locate the receipt and temperature *data logger*. You must verify that the recorded temperature meets the specifications for its transport and storage. You will verify the contents (PI) with what is reported on the document. If the document matches the contents, you will sign the receipt and send it to the sponsor. If not, you will notify the sponsor.

Storage and safeguarding are the responsibility of the research center. The medication must be kept in a secure area with restricted access.

Storage temperature should be 2° to 30°C.

Upon receipt at the center and until the IP is out of stock, the research center is required to review the IP's storage conditions daily and manually record, in the designated format, the temperature recorded by the *data logger* (current, minimum, and maximum temperatures). *These data will be reviewed by the clinical monitor during monitoring visits according to the records stored in the data logger's memory.*

In the event of material loss, this must be documented in the input and output log along with a clear description of the mechanism by which the loss occurred.

Upon completion of the protocol, all study materials will be retrieved by the sponsor as part of the final visit. The final return of materials will be made by the principal investigator or the person designated by the principal investigator to return materials at the end of the study.

The sponsor reserves the right to initiate civil and criminal action against the principal investigator in the event of undocumented material missing at the end of the study.

6.3 Concomitant treatments and medications (permitted and prohibited)

Any medication used, in addition to appearing in the clinical note, must be recorded in the concomitant medications section of the electronic Case Report Form (eCRF).

Permitted medications:

- Ophthalmic:

All permitted ophthalmic medications administered during the study must be after the last application of the study or reference treatments, waiting a minimum of 10 minutes. This is to avoid treatment interactions with the tear film, based on the physiological tear flow rate and volume. [24]

- Tetracaine 0.5%
- Tropicamide 0.8% / Phenylephrine 5%
- Any antibiotic
- β -blocker*

- α -agonist*
- Any topical steroid
- Any topical nonsteroidal anti-inflammatory drug

*Topical antihypertensives are permitted after the 1st safety visit; they cannot be used prophylactically.

- Administered by a route other than ophthalmic:
 - The use of medications for the treatment of chronic diseases that do not appear as an exclusion criterion (e.g., medications for the treatment of systemic arterial hypertension) will be permitted.
 - Medications with ocular hypotensive action, such as acetazolamide or mannitol, are prohibited as prophylactic agents; their use may be permitted after 1st safety visit.
 - Any medication whose effect may be susceptible to modifying any of the efficacy, safety or tolerability parameters of this research protocol must be notified to the clinical monitor or the sponsor's clinical team to determine the appropriateness of the participant's admission, continuation or elimination as appropriate.

Prohibited medications:

- Any medication with ophthalmic application that is not on the list of permitted medications
- Systemic immunomodulators
- Anticoagulants
- Medications with non-ophthalmic applications and with hypotensive action at the ocular level

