Investigational product, dosage and route of administration:

- PRO-149. Sodium hyaluronate 3%. Viscoelastic solution in a pre-filled syringe. Laboratorios Sophia, S.A. de C.V.
- Posology: Enough to create the desired intraocular space and perform the required intraocular maneuvers.
- Route of administration: Intraocular, in the anterior chamber.

Comparator product, dose and route of administration:

- Healon® EndoCoat. Sodium hyaluronate 3%. Viscoelastic solution in a pre-filled syringe. Johnson & Johnson Vision Surgical.
- Posology: Enough to create the desired intraocular space and perform the required intraocular maneuvers.
- Route of administration: Intraocular, in the anterior chamber.

Duration of treatment:	Approximate duration of the subject in the study:
Transsurgical.	45 days.

Evaluation criteria:

Primary outcome variables:

- Changes in CEC density.
- IOP.

Secondary outcome variables:

- Incidence of adverse events (AEs).
- Changes in corneal thickness.
- Cellularity in AC.
- Flare in AC.
- Best corrected visual acuity (BCVA).

[figure not shown]
Exploratory outcome variables:

- Investigator's report of the transsurgical evaluation.

Statistical methodology:

Data will be expressed with measures of central tendency: mean and standard deviation for quantitative variables, while qualitative variables will be presented as frequencies and percentages. The Kolmogorov-Smirnov (KS) and Shapiro-Wilk (SW) tests will be performed to determine whether the distribution is normal for the results obtained in each study group ($p > 0.05$). If normality is observed in the data, the Student's t-test for independent groups will be used to evaluate differences between groups on quantitative variables, while intragroup differences will be analyzed using the Student's t-test for repeated measures. If $p < 0.05$ for both KS and SW, the statistical analysis will be performed using the Mann-Whitney U test for differences between groups on quantitative variables, while intragroup differences will be analyzed using the Wilcoxon rank test. Differences between qualitative variables will be analyzed using the χ^2 (chi-square) test or Fisher's exact test. An $\alpha \leq 0.05$ will be considered significant.

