3.2 Specific objectives

- To compare the safety of OVD PRO-149 versus Healon® EndoCoat in cataract phacoemulsification surgery and intraocular lens implantation, through changes in pre and postoperative CEC density.
- To compare the safety of OVD PRO-149 versus Healon® EndoCoat in cataract phacoemulsification surgery and intraocular lens implantation, through changes in IOP.

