10.1.2 Data interpretation

The results of continuous quantitative variables will be presented in measures of central tendency: mean, standard deviation and ranges.

KS and SW tests will be performed, as applicable, to determine whether the distribution presents normality in the results obtained in each study group. [44]

If normality of the data is observed ($p > 0.05$; for KS and SW), the statistical analysis of the continuous quantitative variables to find significant differences (p) will be as follows:

- Intra-group analysis: will be determined using the Student's t-test for repeated measures.
- Between-group analysis: differences between groups will be analyzed using Student's t-test for independent groups.

For $p < 0.05$ in KS and SW, the statistical analysis of continuous quantitative variables to find significant differences (p) will be as follows:

- Intra-group analysis: will be determined using the Wilcoxon rank test. [45]
- Between-group analysis: differences between groups will be analyzed using the Mann-Whitney U statistic.

The level of difference to consider significance will be an α of 0.05 or less [46].

The results of the nominal and ordinal qualitative variables will be presented in frequencies, proportions and percentages.

Statistical analysis to identify significant differences in qualitative variables will be performed by creating 2x2 contingency tables and will be carried out as follows:

- Intra-group differences: will be determined by the McNemar test [47], which is applied to 2x2 contingency tables with a dichotomous trait and pairs of matched subjects to determine whether the marginal frequencies of row and column are equal (marginal homogeneity).
- Difference between groups: Differences between groups will be analyzed using Pearson's X^2 test or Fisher's exact test when expected values are less than 5.

The level of difference to consider significance will be an α of 0.05 or less.

For the reporting of adverse events, participants who were randomly assigned to an intervention group after application of the investigational product will be considered.

The final results report will be displayed in tables or graphs, as appropriate.

The investigational product will be considered safe when there are no clinical and statistical differences in all primary outcome variables, with respect to its comparator (Healon EndoCoat®).

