10.1.3 Procedure for handling missing data

The safety assessment will include in the analysis all subjects who have been exposed to any of the interventions, regardless of the visit at which they were eliminated from the study (ITT; intention-to-treat population).

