10.1.5 Subjects included in the analysis

Those subjects who complete all their visits will be included in the statistical analysis to meet the study objective (PP; per-protocol population).

The variables, method and scales for their measurement are described in detail below.

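### Primary IOP: no deciding visit is named, the measure is inconsistent (raw or change), the between-arm test ignores screening IOP, and section 10 has no rule for readings after permitted IOP-lowering drugs

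*Combined protocol and SAP*

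**What the plan says.** **Role and timing.** Sections 1.1 and 7.4.1 list two primary variables: change in endothelial cell density, and IOP. The study schedule (1.3) and Table 3 (7.4.4) place IOP at screening, Day 1, Day 8±2 and Day 29±2. Endothelial density has a single postoperative reading, at the final visit.

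**Measure.** Sections 1.1, 7.4.1 and Table 3 give IOP in mmHg, with no mention of change. Section 3.2 compares the products "through changes in IOP". It does not give the reference visit or say whether the change is absolute or a percentage.

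**Test and decision rule.** After a normality check, Student's t-test for independent groups "will be used to evaluate differences between groups on quantitative variables" (1.1). Without normality, "differences between groups will be analyzed using the Mann-Whitney U statistic" (10.1.2). The product is considered safe when there are "no clinical and statistical differences in all primary outcome variables" (10.1.2). No clinical threshold for IOP is given.

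**IOP-lowering drugs.** Section 6.3 states: "Topical antihypertensives are permitted after the 1st safety visit". Under non-ophthalmic routes it says that systemic agents such as acetazolamide or mannitol may also be permitted from that point. A further item in the same block requires drugs that could alter study parameters to be notified, so that the sponsor's side can decide on "admission, continuation or elimination as appropriate".

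**Populations.** Section 10.1.5: "Those subjects who complete all their visits will be included in the statistical analysis to meet the study objective". Section 10.1.3 puts into the safety assessment "all subjects who have been exposed to any of the interventions, regardless of the visit at which they were eliminated from the study".

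**The concern.** The safety verdict turns on IOP, yet the plan does not fix which postoperative reading, or which function of it, is compared. Two analysts following the text could test one visit or three, and raw values or changes, and reach different verdicts. The t-test and Mann-Whitney test also leave screening IOP unused, except through subtraction if the change reading is taken.

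The later readings raise a further question. Day 8 and Day 29 IOP may be measured after IOP-lowering drugs chosen by investigators who know the allocation (7.3). Section 10 does not say whether such readings are used as observed, set aside or handled in some other way. At stake are the reproducibility of the primary IOP verdict and the precision of the estimate behind it.

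**Working it through.** The plan gives no IOP calculation to reproduce. Section 10.2.2 sizes the trial on endothelial cell loss, and no IOP SD, correlation or margin appears anywhere.

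**Inputs from the documents:** 18 eyes per arm (10.2.1); alpha 0.05 per test (10.1.2); three postoperative IOP visits (1.3, Table 3).

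**Assumed inputs:** IOP SD 3, 4 or 5 mmHg, equal at all visits; correlation between visits 0 to 0.7; correlation between screening and the postoperative visit 0.3 to 0.7; a clinical threshold of 3 mmHg where one is applied.

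**1. Every postoperative visit counts, identical products**

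Independent visits: 1 − 0.95³ = 0.143. The other rows come from simulated trials (60,000 per setting, t-tests, equal correlation between visits).

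| Inter-visit correlation | At least one p < 0.05 |
|---|---|
| 0 | 0.142 |
| 0.3 | 0.136 |
| 0.5 | 0.126 |
| 0.7 | 0.113 |

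If an observed difference of at least 3 mmHg is also required, the range is 0.007 to 0.009 at SD 3, 0.056 to 0.068 at SD 4 and 0.103 to 0.130 at SD 5.

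**2. Raw or change**

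In 20,000 simulated trials per setting with no true effect (14 or 18 per arm, correlation 0 to 0.9), the raw and change tests at a single visit disagree on significance in about 7% to 9% of trials.

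**3. Precision at one postoperative visit, 18 per arm, SD 4**

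- Raw: t(34) × SD × √(2/18) = 2.032 × 4 × 0.3333 = 2.71 mmHg.
- Change: the raw value × √(2(1 − r)).
- ANCOVA: t(33) × SD × √(1 − r²) × √(2/18) × √(1 + 1/32), with t(33) = 2.035.

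| Screening correlation r | Raw | Change | ANCOVA |
|---|---|---|---|
| 0.3 | 2.71 | 3.21 | 2.63 |
| 0.5 | 2.71 | 2.71 | 2.39 |
| 0.7 | 2.71 | 2.10 | 1.97 |

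ANCOVA is narrowest in every row. The values scale with SD. At SD 3, raw is 2.03 and ANCOVA 1.97, 1.79, 1.48. At SD 5, raw is 3.39 and ANCOVA 3.28, 2.98, 2.46.

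**4. Skewed IOP**

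Section 2.2.2 reports IOP of 30 mmHg or more in 7.5% and 10.5% of subjects in an earlier trial. Lognormal postoperative IOP with mean 18 mmHg (assumed) set to those two rates gives this power for a 3 mmHg difference:

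| Screening correlation r | Rate ≥ 30 mmHg | ANCOVA | Mann-Whitney |
|---|---|---|---|
| 0.3 | 7.5% | 0.228 | 0.247 |
| 0.3 | 10.5% | 0.164 | 0.185 |
| 0.7 | 7.5% | 0.341 | 0.254 |
| 0.7 | 10.5% | 0.243 | 0.196 |

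Across the lognormal settings examined (means 18 and 22 mmHg), ANCOVA's type I error stayed between 0.046 and 0.052.

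**5. IOP-lowering drugs**

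Read together, 6.3 and section 10 show one open point and one conflict. Drugs are permitted after Day 1, and section 10 defines populations but no handling of the readings. Section 6.3 also lists non-ophthalmic drugs with ocular hypotensive action as prohibited, without the exception it makes for them a few lines earlier.

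**The case against.** **The measure is stated.** Section 3.2 does say change, so a reader who infers that no measure is given goes too far. The supportable statement is that the sections disagree and that change is not defined.

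**An all-visits reading is cautious.** Table 3 lists every visit and 10.1.2 requires no difference in all primary variables, so testing all three is a natural reading. Its error falls against the product. This stands: a reader might infer that the missing visit makes a false declaration of safety likelier, and the calculation does not show that.

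**Drug use could mask a real difference.** This is possible if a later visit decides and the difference persists. Its size depends on Day 1 mean and SD, on who is treated and on the drug effect, and the documents supply none of these for this trial. Section 2.4.1 also calls the IOP rise transient, so Days 8 and 29 may show little either way. No figure is offered.

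**Treated eyes might be eliminated.** A reader might infer this from 6.3. The notification and elimination item is printed under non-ophthalmic routes, while topical agents are permitted outright after the 1st safety visit. As printed, it does not clearly reach eyes given topical drugs, although it opens by referring to any medication.

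**ANCOVA is a preference.** An unadjusted test is valid in a randomized trial, so ANCOVA brings precision and does not correct an error. The SD is also assumed: the skewed model in step 4 implies SDs of 7.8 and 9.9 mmHg, which would widen every interval. At a given correlation, the ratio between methods does not depend on SD.

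**Existing safeguards.** Analysts are blinded (10.1.1), concomitant drugs are recorded (6.3), peaks of 30 mmHg or more are adverse events (7.4.4.2), and 10.1.3 keeps all exposed subjects in the safety assessment. These reduce bias but do not say which IOP result decides.

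**Conclusion.** The point holds in this form: the deciding IOP visit is not named, the measure differs between sections, the planned test leaves screening IOP unused, and section 10 gives no rule for Day 8 and Day 29 readings after permitted IOP-lowering drugs.

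Testing all three visits carries about an 11% to 14% chance of a false IOP difference on p alone. With an added 3 mmHg threshold it is under 1% to 13%, depending on SD. At SD 4, ANCOVA cuts the half-width from 2.7 mmHg to 2.6, 2.4 or 2.0 at r = 0.3, 0.5 or 0.7. These sizes rest on assumed SDs and correlations; the gaps in the text do not.

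A reader might also infer that Day 1 must be the deciding visit. It is a reasonable candidate, as the only scheduled postoperative reading before IOP-lowering drugs are permitted. The documents do not compel it, and it would take later visits out of a safety verdict. The point should be settled before analysis, but it does not prevent the trial from running.

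**What to change.** 1. In 1.1, 3.2, 7.4.1, Table 3 and 10.1.2, use one IOP measure: postoperative IOP compared between arms by ANCOVA with screening IOP as covariate, reported as a difference in mmHg with its 95% CI. State that this replaces the normality-gated tests for this variable, with a rank-based sensitivity analysis.
2. In 10.1.2, prespecify which visit or visits decide the safety rule and, if more than one, how they combine. The choice is the sponsor's.
3. In 10.1.5, state that the IOP comparison uses all exposed eyes, in line with 10.1.3. In section 10, state how readings taken after IOP-lowering drugs are analysed.
4. Report by arm the proportion of eyes with IOP of 30 mmHg or more, or any IOP-lowering drug, since surgery. Both are already recorded.
5. Reconcile the two statements in 6.3 on systemic IOP-lowering drugs. No clinical rule is proposed here.

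**Cost.** Text edits only, with no new visits or data, but section 11.2 requires committee review and COFEPRIS authorisation. ANCOVA has about 2 points less power than Mann-Whitney if IOP is strongly skewed and the screening correlation is low. Fewer deciding visits make it easier to pass. Even one IOP test plus the endothelial test leaves 1 − 0.95² = 9.75% for a false difference on p alone, if independent. The change does not cure low power or the reading of non-significance as safety.

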6.4 Procedure for monitoring and measuring adherence

For over four decades, numerous investigations have been conducted on the appropriate way to measure and quantify medication adherence, however, none has reached a consensus to establish itself as the gold standard, both in cross-sectional and longitudinal studies. [25, 26, 27, 28, 29, 30, 31, 32]

Due to the characteristics of the study, which evaluates the use of a device during a surgical procedure, the IP's adherence is directly dependent on the principal investigator's (PI) application during surgery. This rules out adherence errors such as applications outside the eye or forgetting to apply them (the surgical procedure cannot be performed without the use of OVDs). There is no predetermined dosage, so the quantity (volume of the syringe applied) to be used will be customized for each surgical event at the PI's discretion. Adherence will be measured by the clinical monitor during monitoring visits by counting the syringes used.

However, adherence to concomitant treatment (Ciprofloxacin 0.3%/Dexamethasone 0.1% ophthalmic solution) will be measured, as adherence is critical for managing postoperative inflammation; such inflammation could be a confounding factor in the evaluation of study variables.

There are different procedures for measuring adherence to pharmacological interventions. The most common procedure involves self-reports, which include patient interviews, questionnaires, and self-monitoring diaries. Their strengths are speed, flexibility, low cost, and ease of implementation; they have a high degree of specificity for non-adherence; however, their sensitivity and reliability for adherence are low. [32, 33]

Biochemical measurement of the drug, or its metabolite, is one of the methods that best confirms drug use. However, in addition to being costly and impractical, it is of little use in ophthalmic applications, as

peripheral concentrations may be undetectable; and samples from other tissues require more invasive methods that would not be advisable. [32]

Medication counting is another way to measure adherence. Classically referred to as "pill counting," in ophthalmology it is translated as the weight of the bottle. This is a simple, inexpensive, and noninvasive method. The main disadvantages of this method are: 1. It cannot confirm the application of the medication (it could have been intentionally dropped or instilled outside the eye), and 2. It depends on the subject bringing the medication back. [32, 33]

Adhesion assessment will be based on the bottle's weight and will be performed taking into account the following information: drop weight, initial container weight, final container weight, and the total number of applications. The following simplified formula will be used:

$$Ad = \frac{(P_i - P_f)100}{P_T}$$

Where:

Ad = adhesion

P_i = weight of the container delivered to the subject at the beginning

P_f = weight of the container returned by the subject

P_T = weight of the dosage indicated for the investigational products

$$P_T = (P_g)G$$

Where:

P_g = weight of one drop of the medicine, determined by the research and development department

G = number of applications indicated for the investigational products

Containers that are not physically intact will not be considered for adherence calculations. Subjects who do not return the concomitant treatment container at the final visit will be considered non-adherent.

There is no standardized parameter to define adequate adherence; this must be defined and outlined by the objectives of the particular research. [32]

For this study, a minimum adherence of 60% will be considered necessary to meet the research objectives. Therefore, subjects with less than 60% adherence will be included in the intention-to-treat population.

